I have read this protocol and agree that it contains all necessary details for carrying out this study. I will conduct the study as outlined herein and will complete the study within the time designated. I will comply with all relevant ICH and GCP requirements during the conduct of this study.

I will provide copies of the protocol and all pertinent information to all individuals responsible to me who assist in the conduct of this study. I will discuss this material with them to ensure that they are fully informed regarding the investigational product (IP) and the conduct of the study.

Investigator's Signature

Date

Name of Investigator (Typed or Printed)

Institution, Address*

Phone Number*

Coordinating Investigator's Signature (where required)

Date

Name of Coordinating Investigator (Typed or Printed)

Institution

*If the address or phone number of the investigator changes during the course of the study, written notification will be provided by the investigator to the sponsor and will not require protocol amendment(s).

Protocol Synopsis	
Name of Sponsor/Company:	CorMedix Inc.
Name of Finished Product:	Neutrolin®
Name of Active Ingredients:	Taurolidine (1.35% (13.5 mg/mL), 3.5% (26.1 mg/mL) citrate and heparin 4,000 USP Units/4 mL (1,000 USP Units/mL))
Title of Study:	A Phase 3, prospective, multicenter, double-blind, randomized, active control study to demonstrate the safety and effectiveness of Neutrolin® in preventing catheter-related bloodstream infections in subjects receiving hemodialysis therapy as treatment for end stage renal disease.
Protocol No:	LOCK-IT-100
Investigators:	Multicenter
Study centers:	Up to 85 centers in the US
Study duration:	Subjects will be followed until a CRBSI has occurred, the catheter is removed, the subject withdraws, or the study is ended.
Objectives:	The primary objective of this study is to demonstrate the efficacy and safety of Neutrolin® as a catheter lock solution (CLS) for prevention of catheter-related bloodstream infection (CRBSI) in subjects receiving hemodialysis (HD) for the treatment of End Stage Renal Disease (ESRD) when compared with heparin 4,000 USP Units/4 mL (1,000 USP Units/mL). The study will demonstrate whether Neutrolin® is superior to the active control heparin in reducing the incidence of CRBSI.
Study Design:	
This is a randomized, double-blind, active control, parallel-arm, multicenter study. Approximately 900 subjects will be randomized in a 1:1 ratio to receive either Neutrolin® or the active control heparin (Heparin sodium USP 1,000 units/mL, Benzyl alcohol 9.45 mg/mL and Sodium chloride 9.0 mg/mL) as a CLS. Neutrolin® or heparin will be instilled into central venous HD catheters at the discontinuation of all dialysis sessions and will be withdrawn prior to the initiation of the next dialysis session.
 
All subjects will receive standard of care consistent with clinical practice guidelines recommended by KDOQI for the placement, care and use of central venous catheters (CVC) for HD therapy.

Number of subjects planned and assignment to treatment:	Approximately 900 randomized subjects are planned for this trial. In this study, one-half of the subjects (450 subjects) will receive Neutrolin® and the other half will receive heparin 4,000 USP Units/4mL (1,000 USP Units/mL) with benzyl alcohol preservative as a comparator. Subjects will be assigned in a 1:1 ratio using permuted blocks without

Protocol Synopsis	
Name of Sponsor/Company:	CorMedix Inc.
Name of Finished Product:	Neutrolin [®]
Name of Active Ingredients:	Taurolidine (1.35% (13.5 mg/mL), 3.5% (26.1 mg/mL) citrate and heparin 4,000 USP Units/4 mL (1,000 USP Units/mL))
additional stratification for both groups. For the purpose of this blinded study, the term investigational product will refer to either Neutrolin [®] or the comparator.	

Diagnosis and main criteria for inclusion and exclusion:
 
Adult subjects (≥ 18 years) with ESRD undergoing chronic HD with a permanent, tunneled silicone or polyurethane catheter that has demonstrated the ability to achieve a minimum blood flow of at least 250 mL/min for at least two consecutive dialysis sessions to enable successful HD. Subjects may not be entered into this trial if they have been treated with antibiotics within 14 days of randomization for any systemic infection or have active exit site infection around the CVC, or received thrombolytic treatment within 30 days of randomization.
	

Test product, dose and mode of administration:
 
Neutrolin[®] and the active control will be packaged in identical vials, and will be used as a catheter locking solution for HD catheters in the following manner:
 
 • Day 1 (day of first administration of blinded, randomized therapy): following randomization and entry into the trial, instill CLS following the index HD episode, as described in the protocol; • Subsequent HD sessions: CLS will be removed prior to HD and instilled in the catheter following the HD session, as described in the protocol. 	

Duration of treatment:
 
Subjects are to be followed from randomization until either:
 
 • The development of a CRBSI; • Withdrawal from the study; • Catheter removal; or • The end of the study, whichever occurs first. 
The study has been designed to continue until approximately 56 subjects have experienced a CRBSI. It is expected that some subjects may be treated for 2 years or more.
	

Reference therapy, dose, and mode of administration:
 
Heparin 4,000 USP Units/4mL (1,000 USP Units/mL) as a CLS for the active control.
	

Criteria for evaluation:
 
Primary endpoint: Time to CRBSI:
 
The primary objective of this study is to demonstrate the effectiveness of Neutrolin[®] as a CLS in ESRD subjects undergoing HD treatment using a permanent, cuffed, tunneled
	

Protocol Synopsis	
Name of Sponsor/Company:	CorMedix Inc.
Name of Finished Product:	Neutrolin®
Name of Active Ingredients:	Taurolidine (1.35% (13.5 mg/mL), 3.5% (26.1 mg/mL) citrate and heparin 4,000 USP Units/4 mL (1,000 USP Units/mL))

silicone or polyurethane HD catheter. The study will evaluate whether Neutrolin® is superior to the active control heparin by documenting the time to CRBSI and consequently delaying the time until the occurrence of CRBSI.
 
The definition of CRBSI used in this study requires that the same organism is grown from at least one blood culture from:
 
 • a peripheral site or bloodline sample 
and
 
 • either the arterial or venous catheter hub (or the venous or arterial dialysis circuit blood lines if on dialysis). 
Blood cultures must be taken from two sites to enhance the validity of the culture testing results. One aerobic and 1 anaerobic blood culture bottle should be taken from each site.
 
If the subject has clinical symptoms, while on or off dialysis, blood cultures will be obtained using peripheral venipuncture from a source not intended for future vascular access, and the venous or arterial hub of the HD CVC (or the venous or arterial dialysis circuit blood line if on dialysis). If a peripheral site is not available, as soon as the patient is evaluated, blood cultures can be obtained from both the venous and arterial hubs of the HD CVC (or the dialysis circuit blood lines if on dialysis), preferably before the study subject receives antibiotics. Ten to twenty mL of blood should be collected, without discarding any of the CLS.
 
Necessary clinical indication for suspicion of infection includes the following:
 
One of the following symptoms:
 
 • Fever (defined as $\geq 37.8^{\circ}$ C) or • Rigors, defined as shivering from a feeling of being cold, often with copious sweating, as documented by a medical professional 
OR two or more of the following symptoms:
 
 • Tachycardia defined as a heart rate greater than 100 beats per minute • Tachypnea, as defined as a RR greater than 24 breaths per minute 	

Protocol Synopsis	
Name of Sponsor/Company:	CorMedix Inc.
Name of Finished Product:	Neutrolin®
Name of Active Ingredients:	Taurolidine (1.35% (13.5 mg/mL), 3.5% (26.1 mg/mL) citrate and heparin 4,000 USP Units/4 mL (1,000 USP Units/mL))

 • Low blood pressure as defined as a systolic blood pressure less than 90, as measured by a clinician (RN or MD) with a BP cuff, or a decrease in blood pressure greater than 30 mmHg • An obvious change in mental status from previously documented baseline. 
All attempts will be made to document as many signs and/or symptoms as possible at the time of suspected CRBSI.
 
An investigator may choose to obtain blood cultures on other suspicions of CRBSI, but the CRBSI case definition requires the clinical indication for suspicion of infection criteria listed above in addition to the blood culture criteria listed above. An alternate source of infection should not be clinically suspected.
 
Clinical Adjudication Committee
 
While sites will seek to identify that a CRBSI is present and will be responsible for collecting the clinical data and blood cultures as outlined in the protocol, each case will be reviewed by a Clinical Adjudication Committee (CAC) for the final assessment of CRBSI status. The CAC is a multi-disciplinary committee of specialists who will review both the clinical documentation as well as the blood culture results to determine if the case is a CRBSI. However, because the CAC determination is based on data obtained from the clinical sites, and the review cannot be initiated without blood culture results, it is imperative that the sites follow the protocol definition of CRBSI, and collect blood cultures when a CRBSI is suspected.
 
Secondary Endpoints
 
 1. Catheter Removal: Catheter removal for any reason, for example as a result of CRBSI, catheter malfunction, or the catheter is no longer needed for hemodialysis, during the follow up period of the trial. 2. Catheter Patency: Loss of catheter patency following enrollment in the study. Loss of catheter patency is defined as required use of a tissue plasminogen activating factor (tPA) or removal of catheter due to dysfunction. 	

Protocol Synopsis	
Name of Sponsor/Company:	CorMedix Inc.
Name of Finished Product:	Neutrolin®
Name of Active Ingredients:	Taurolidine (1.35% (13.5 mg/mL), 3.5% (26.1 mg/mL) citrate and heparin 4,000 USP Units/4 mL (1,000 USP Units/mL))

Statistical Methods: Subject demographic, clinical and laboratory data will be summarized by treatment arm using descriptive statistics.
 
Primary effectiveness analysis:
 
CRBSI The time to CRBSI will be compared between the treatment arms using a log-rank test at a 2-sided 5% alpha level. The null hypothesis is that there is no difference in the risk of CRBSI over time between the two treatment groups. Subjects will be treated as censored in this analysis if the catheter is removed for reasons other than CRBSI (e.g., catheter removed because no longer required) or follow-up for CRBSI discontinues.
 
The primary analysis will be based upon the Full Analysis Population defined as randomized subjects receiving at least one dose of assigned treatment. While testing will be based upon the log-rank test, the estimated treatment effect will be the incidence of CRBSI calculated as the number of subjects with a CRBSI episode divided by the duration of follow-up over subjects (follow-up will be based upon the same time as used for the log-rank test). The rate will be presented as the event rate per 1,000 days with 95% confidence interval presented for the comparison of rates between the treatment arms. This confidence interval will be derived assuming that the number of days until CRBSI follows an exponential distribution.
 
Similar methods of analysis will be used to estimate the overall rate of catheter loss for any reason and the rate of loss of catheter patency. The fixed sequence testing procedure will be used for the comparison of the two treatments with respect to the effectiveness endpoints. Therefore, the analysis comparing the two treatments for catheter loss for any reason will be formally conducted only if the analysis for the primary effectiveness endpoint yields a statistically significant result favoring Neutrolin®, and the analysis comparing the two treatments for loss of patency will be formally conducted only if the analysis for catheter loss for any reason also yields a statistically significant result favoring Neutrolin®.
 
Sample Size This trial has been designed to achieve 80% power for the comparison between treatment
	

Protocol Synopsis	
Name of Sponsor/Company:	CorMedix Inc.
Name of Finished Product:	Neutrolin [®]
Name of Active Ingredients:	Taurolidine (1.35% (13.5 mg/mL), 3.5% (26.1 mg/mL) citrate and heparin 4,000 USP Units/4 mL (1,000 USP Units/mL))

arms subject to the following specifications: testing will be conducted at a 2-sided overall 5% alpha level, Neutrolin[®] is associated with a 55% reduction in the risk (i.e., incidence) of CRBSI relative to the control arm, and one interim analysis will be performed at the midpoint of the trial with adjustment of the alpha level using the method of Pocock. Fifty-six CRBSI events in total will be needed to achieve the desired power, and the event rates will be monitored over the course of the trial to determine the times of the interim and final statistical analyses. It is expected that approximately 900 subjects will be randomized for this trial.
 
Safety analyses
 
The safety information will be presented based upon descriptive analysis characterizing the relative rates of deaths, adverse events, serious adverse events and loss of patency between the treatment arms. The treatment arms will also be evaluated with respect to changes in laboratory parameters.
	

TABLE OF CONTENTS

1.0	LIST OF ABBREVIATIONS AND DEFINITIONS OF TERMS	13
2.0	INTRODUCTION.....	15
2.1	Clinical Need for Prevention of Catheter-Related Bloodstream Infections.....	15
2.2	Background on Catheter Lock Solutions	16
2.3	Overview and Rationale for Use of Neutrolin® as a Catheter Lock Solution	20
2.4	Safety of Neutrolin®	22
2.5	Rationale for the Formulation of Neutrolin®	24
3.0	STUDY OBJECTIVES.....	25
3.1	Primary Objectives	25
3.2	Safety Objectives.....	25
3.3	Primary Endpoint	25
4.0	INVESTIGATIONAL PLAN	27
4.1	Overall Study Design and Plan.....	27
4.2	Discussion of Study Design	28
5.0	SELECTION OF STUDY POPULATION.....	29
5.1	Inclusion Criteria	29
5.2	Exclusion Criteria	30
5.3	Study Completion, Early Withdrawal, New Catheter Placement.....	31
6.0	STUDY TREATMENTS	33
6.1	Identity of Investigational Products	33
6.2	Blinding	33
6.3	Treatments to Be Administered	33
6.4	Method of Assigning Subjects to Treatment Group	34
6.5	Selection of Neutrolin® Composition and Control	34
6.6	Selection and Timing of the Catheter Lock Solution	34
6.7	Prior and Concomitant Therapy/PROCEDURES.....	34
6.8	Standard of Care for Prevention of CRBSI.....	35
6.9	Standard of Care for Hemodialysis	35
6.10	Treatment Compliance.....	35
6.11	Investigational Product Accountability	36
7.0	EFFECTIVENESS AND SAFETY VARIABLES	37
7.1	Schedule of Assessments.....	37
7.2	Screening/Baseline Assessments	44

7.3	Effectiveness Measurements	45
7.4	Safety Measurements	47
7.5	Appropriateness of Measurements	52

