4.0 INVESTIGATIONAL PLAN

4.1 OVERALL STUDY DESIGN AND PLAN

This is a randomized, double-blind, active-control, parallel-arm, multicenter study. Subject will be followed until a CRBSI has occurred, the catheter is removed, the subject withdraws, or the study is ended.. Approximately 900 subjects with end stage renal disease undergoing HD using a tunneled silicone or polyurethane HD catheter are anticipated be randomized from up to 85 centers in the United States.

Subjects will attend a screening visit up to fourteen days prior to dosing. At this visit entry criteria will be checked and baseline characteristics will be collected. If the subject meets eligibility criteria, at the Baseline Visit, subjects will be randomized and begin the first day of dosing. Study visits will occur on dialysis treatment days. Every four weeks at one of these dialysis visits a more extensive visit will occur including the collection of vital signs and labs, as outlined in section 7.1.5. Subjects are to remain in the study until they have met the primary endpoint, withdrawn from the study, their catheter is removed, or until the study completes.

All subjects will receive standard of care therapy consistent with current practice guidelines, and will be randomized to either Neutrolin[®] (1.35% taurolidine, 3.5% citrate, heparin 4,000 USP Units/4mL (1,000 USP Units/mL)) or the active control heparin 4,000 USP Units/4mL (1,000 USP Units/mL) in a 1:1 ratio.

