7.3 EFFECTIVENESS MEASUREMENTS

Effectiveness assessments are based on the hypotheses that Neutrolin[®] is superior to heparin and will decrease the risk of CRBSI. CRBSI is the primary endpoint for this trial.

For the purposes of this study, once the subject has been randomized and has received at least one instillation of the assigned lock solution, all episodes that satisfy the definitions in section 7.3.1.1 will be considered definite episodes of CRBSI. Once the infection is confirmed as a CRBSI, the subject will be considered to have satisfied the infection endpoint and will be considered to have completed the study. The subject will receive standard of care therapy for CRBSI and the decision as to removal of the catheter will be left to the PI, although KDOQI guidelines should be followed. The use of an antibiotic CLS to treat the catheter following a documented episode of CRBSI will be discouraged.

Should a subject receive treatment with an antibiotic CLS following confirmation of one positive blood culture, this subject would be discontinued from the study. Documentation of the reason(s) for removal or retention of the catheter following an episode of CRBSI will be recorded in the case report forms.

Blood flow will be monitored during each dialysis session to ensure adequate blood flow is present for successful dialysis.

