1.2 Study Design

This is a randomized, double-blind, active control, parallel-arm, multicenter study. Approximately 900 subjects will be randomized in a 1:1 ratio to receive either Neutrolin[®] or the active control heparin (Heparin sodium USP 1,000 units/mL, Benzyl alcohol 9.45 mg/mL and Sodium chloride 9.0 mg/mL) as a CLS. Neutrolin[®] or heparin will be instilled into central venous HD catheters at the discontinuation of all dialysis sessions and will be withdrawn prior to the initiation of the next dialysis session. All subjects will receive standard of care consistent with clinical practice guidelines recommended by the Kidney Disease Outcomes Quality Initiative (KDOQI) for the placement, care and use of central venous catheters (CVC) for HD therapy.

The primary endpoint is the presence or absence of a CRBSI (analysis will be made using the time to CRBSI). Subjects are to be followed from randomization (HD catheter will be in place prior to randomization) until occurrence of CRBSI, catheter removal, or the end of the study, whichever occurs first. The study has been designed to continue until approximately 56 subjects have experienced a CRBSI. It is expected that some subjects may be treated for 2 years or more.

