2.4.2 Secondary Endpoint Analyses

Time until catheter removal for any reason and time to loss of catheter patency will be analyzed using similar methods as for the primary analysis in the Full Analysis Population. Loss of catheter patency is defined as required use of a tissue plasminogen activating factor (tPA) or removal of the catheter due to dysfunction. For these endpoints, subjects will be considered censored as of their final clinical assessment if the event of interest is not observed. Otherwise, the event time will be the number of catheter-days between randomization and the event. The fixed sequence testing procedure will be used for the comparison of the two treatments with respect to the efficacy endpoints. Therefore, the analysis comparing the two treatments for catheter removal for any reason will be formally conducted only if the analysis for the primary effectiveness endpoint yields a statistically significant result favoring Neutrolin®, and the analysis comparing the two treatments for loss of patency will be formally conducted only if the analysis for catheter loss for any reason also yields a statistically significant result favoring Neutrolin®.

In addition to basic descriptive statistics, the rates per 1000 catheter-days of follow-up will be presented for both endpoints. Also, the reason for catheter loss will be summarized by treatment group.

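### Catheter removal, the first secondary endpoint: the SAP addendum lets events run later than censoring, so late risk time depends on the outcome

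*Protocol*

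**What the plan says.** **Endpoint.** The Protocol Synopsis (Secondary Endpoints) defines the first secondary endpoint as "Catheter removal for any reason, for example as a result of CRBSI, catheter malfunction, or the catheter is no longer needed for hemodialysis", occurring "during the follow up period of the trial". SAP 2.3 and addendum 1.1 keep the any-reason definition and the follow-up-period limit.

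**End of follow-up.** Protocol 4.1: "Subject will be followed until a CRBSI has occurred, the catheter is removed, the subject withdraws, or the study is ended". SAP 1.2 follows subjects "until occurrence of CRBSI, catheter removal, or the end of the study, whichever occurs first". Under Protocol 7.3, once a CRBSI is confirmed, "the subject will be considered to have satisfied the infection endpoint and will be considered to have completed the study". The same section leaves the removal decision to the investigator, and the reasons "for removal or retention of the catheter following an episode of CRBSI will be recorded in the case report forms". Protocol 7.1.6 sets a final safety visit 28 (+7) days after the last product is removed, and clinical endpoint events are assessed there.

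**Target period.** SAP 2.6 says that the primary and secondary analyses describe risk over the life of the subject's first on-study catheter.

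**Censoring.** In SAP 2.4.2, "subjects will be considered censored as of their final clinical assessment if the event of interest is not observed"; SAP 3.7.3 repeats this. Neither section defines the final clinical assessment. Addendum 1.1 bases the primary analysis of this endpoint on data through the last patient's last visit (LPLV). Any date of catheter removal makes the subject an event. A subject without one is censored at the earlier of study completion and last study drug dose plus 3 days.

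**Role in testing.** By SAP 2.4.2, the "analysis comparing the two treatments for loss of patency will be formally conducted only if the analysis for catheter loss for any reason" is itself significant in favour of Neutrolin.

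**The concern.** Removal because of CRBSI is named as an event, but it can only follow the CRBSI, and the CRBSI ends the subject's follow-up. No passage says whether a removal after completion counts, or until when.

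The addendum gives an operating rule, but its two halves use different windows. Events are accepted up to LPLV, while censoring falls at completion or three days after the last dose. Past that date, the subjects still in the risk set are those who will later be recorded as removals. Subjects who kept their catheters over the same days contribute no time. A log-rank test and a rate per 1,000 catheter-days both need membership of the risk set not to depend on the future outcome.

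Two things are at stake: the event count and hazard ratio of a formally tested endpoint, and whether the patency test is opened. The problem need not cancel between arms, because the design expects more subjects to complete through CRBSI on heparin than on Neutrolin.

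**Working it through.** **1. Two subjects under the addendum rule.** Both have a CRBSI confirmed on day *t*, so both complete the study on day *t*. Subject A's catheter is removed on day *t + d*. Subject B's is retained.

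- A has a removal date: event on day *t + d*, at risk throughout days *t* to *t + d*.
- B has none: censored at the earlier of day *t* and last dose plus 3 days, so at risk no later than day *t*.

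A and B had the same status on day *t*. Only the later outcome decides who contributes time after it. The same holds for a subject who stops dosing for another reason with the catheter in place (Protocol 5.3.2): a removal during the 28-day safety period is an event, while no removal means censoring three days after the last dose.

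**2. Width of the gap.** The addendum adds three days because the lock is typically withdrawn about then. The final safety visit falls 28 to 35 days after that withdrawal. If removals are recorded only up to that visit, the event window exceeds the censoring window by about 28 to 35 days; if they are recorded later, by more, up to LPLV.

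**3. The same post-CRBSI removal under each text.**

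| Text | Does it count? |
|---|---|
| Follow-up ends at CRBSI (Protocol 4.1, SAP 1.2), read narrowly | No |
| SAP 2.4.2 and 3.7.3 | Yes if the final clinical assessment is the safety visit; no if it is the CRBSI visit |
| SAP 2.6, life of first on-study catheter | Yes |
| Addendum 1.1 | Yes, if the date is in the data through LPLV |

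**4. The plan's own design figures.** These supply the hazard ratio (HR 0.45, from a 55% reduction) and the CRBSI counts (28 and 56). A two-look Pocock design at half and full information has boundary 2.178, nominal level 0.0294, as stated. With 56 events and drift |ln 0.45| × √56 / 2, power is 0.810 against the stated 80%. The point does not depend on this.

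**5. Illustration: all post-CRBSI removals counted, versus none.** From the documents: *C* = 28 CRBSIs at the interim and HR 0.45. Assumed: a share *f* of 0.5 or 1.0 of those catheters is removed; there are 250 or 450 removals for other reasons, equal between arms; the test is two-sided at 0.05 (the documents do not state a separate level for the secondary tests).

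- Split of CRBSIs: heparin 28/1.45 = 19.3; Neutrolin 28 − 19.3 = 8.7. Heparin share 69%.
- HR if all count = (other/2 + *f* × 8.7) / (other/2 + *f* × 19.3). Events = other + *f* × 28.
- Chance of a significant result favouring Neutrolin = Φ(−ln HR × √events / 2 − 1.96).

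| *f* | Other removals | HR | Events | Chance |
|---|---|---|---|---|
| 0.5 | 450 | 229.3/234.7 = 0.977 | 464 | 4.3% |
| 0.5 | 250 | 129.3/134.7 = 0.961 | 264 | 5.1% |
| 1.0 | 450 | 233.7/244.3 = 0.957 | 478 | 7.0% |
| 1.0 | 250 | 133.7/144.3 = 0.926 | 278 | 9.3% |

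If none count, HR is 1.00 and the chance is Φ(−1.96) = 2.5%. Between 14 and 28 events change status, an arm difference of 5 to 11.

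**The case against.** The best defence is that the plan already answers the main question. SAP 2.6 aims at the life of the first catheter, which does not stop at CRBSI. The phrase limiting events to the follow-up period of the trial can be read as the whole trial. The addendum is the later and more specific text, and its event rule is plain. Sites record removal or retention after CRBSI. A removal between onset and confirmation of the infection lies inside follow-up even on the narrow reading. All of this stands. A reader might infer that CRBSI-driven removals drop out of the tested endpoint; under the addendum they do not.

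Other inferences also go too far:

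- *Events have no end limit.* They are bounded by the data through LPLV.
- *The documents provide no source for a removal date after CRBSI.* The completion reason that excludes removal due to CRBSI belongs to the addendum's loss-of-patency rule. The catheter-removal rule uses a separate date of removal.
- *The rule was set with knowledge of results.* Interim analyses of this endpoint went to the DSMB, but Protocol 4.1.2 keeps the unblinded summaries from sponsor staff. Since the SAP's term was undefined, the addendum may simply have made it operational.

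None of this defence reaches the mismatch itself. A clear event rule paired with an earlier censoring rule still makes risk time depend on the outcome.

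**Conclusion.** The point holds as a defect in the counting rule for catheter removal. The any-reason definition and the order of testing are not in question. The mismatch follows from the addendum's text and needs no assumption, although its practical effect depends on how many removals are recorded after completion or last dose plus 3 days. The documents do not give that number.

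The effect is probably modest. With 28 CRBSIs and the assumptions shown, counting all post-CRBSI removals rather than none changes the chance of a nominal win from 2.5% to about 4-9%. That contrast bounds what is at issue for CRBSI subjects; it does not measure the SAP against the addendum, since a removal soon after CRBSI could count under both. Taking the planned 56 CRBSIs raises the top figure to about 23%, but the study was stopped on its 28-event interim and the count through LPLV is not given, so the documents do not support that size. The removal share and the number of other removals are assumptions throughout.

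The point is worth acting on because the endpoint is formally tested and gates the patency test, and the repair is small.

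**What to change.** Apply one cut-off for catheter removal to both event and censoring dates. There are two consistent choices:

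1. Count removals only up to the addendum's censoring date (the earlier of study completion and last dose plus 3 days).
2. Follow every subject for removal to the same later date at which catheter status is known, for example the final safety visit in Protocol 7.1.6, and censor those without a removal there.

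The second fits the synopsis definition and SAP 2.6 better, because it keeps CRBSI-driven removals. Its small downside is that some late removals may occur on a non-study lock. State which choice is the formal analysis and report the other as a sensitivity analysis. Give the number of post-CRBSI removals by arm. If the term final clinical assessment is kept, define it to match.

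The cost is a few sentences and one rerun of an existing log-rank program. Removal or retention after CRBSI and endpoint events at the safety visit are already collected, though removal dates may be less complete after study completion and should be checked.
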